## Data Analysis

### Statistical Analyses and Power

#### Analysis for Specific Aim 1a

The data that will be used in Aim 1a has undergone quality control (QC) as a part of a prior project (IRB #16-004978). For the analysis of heritability captured by common SNPs, we will first estimate the heritability of different measures of AUD treatment response (e.g. length of sobriety, return to heavy drinking or percent days abstinent) explained by common SNPs using the mixed linear model approach implemented in the GCTA software (104). This approach requires more stringent QC than for standard GWAS. Thus, we will begin by performing additional QC in each dataset, which will include: the exclusion of one of each pair of individuals who share more than 2.5% of their genetic material demonstrating distant relatedness, and exclusion of SNPs with Hardy-Weinberg Equilibrium (HWE) p-value  $<10^{-3}$ . Because these methods can produce biased results in the presence of population stratification, these analyses will be performed in an ancestrally homogenous subsample, specifically participants of European Ancestry as they represent the vast majority of the full sample (Table 2). Principal Component Analysis (PCA) will be used to identify outliers for exclusion, ensuring an ancestrally homogeneous subset of participants. The analysis of imputed data will also be performed, as described below; for these analyses only SNPs imputed with very high confidence ( $R^2 > 0.9$ ) will be retained. Following QC, we will use GCTA to calculate the Genetic Relationship Matrix (GRM) and will then use a linear mixed model with residual maximum likelihood (REML) analysis to estimate the variance attributable to the SNPs (i.e. SNP-based heritability) for each treatment

outcome measure. These analyses will include study, and principal components that capture ancestry as covariates. Estimates (and confidence intervals) for the SNP heritability of different outcomes will be compared.

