#### Specific Aim1a:

This aim will use existing data from three prior studies [i.e., The Combined Pharmaco-therapies and Behavioral Interventions conducted in the United States (COMBINE Study)[1], a double-blind, placebo-controlled randomized trial conducted in Germany (PREDICT Study)[2], and “A Pharmacogenomic Probe Study of Acamprosate: Genes Associated with Response” Mayo Clinic Center for the Individualized Treatment of Alcohol

study (CITA); total N=1687], to assess the heritability explained by common single nucleotide polymorphisms (SNPs) and the genetic architecture for different measures of alcoholism treatment response. We will use this data to estimate the heritability of different outcomes in patients treated with acamprosate, placebo and naltrexone (as active drug control) that can be explained by common SNPs. We will also investigate the sources of genetic contribution to different treatment outcomes in terms of the distribution of the genetic signal across minor allele frequencies and functional annotation categories. These analyses may help determine if sobriety or another treatment outcome (e.g. return to heavy drinking) is the most suitable phenotype for subsequent pharmacogenomic analyses of acamprosate treatment response.

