Table 2 Subject Characteristics	COMBINE	PREDICT	CITA
N	1393	426	443
Age, mean(SD)	44.4 (10.2)	45.3 (8.7)	42.1 (11.8)
Sex, N(%) male	955 (69%)	328 (77%)	286 (65%)
Race, N(%) white non-Hispanic	1062 (77%)	426 (100%)	412 (93%)
Baseline Consumption Measures (last 30 days)			
Average drinks per drinking day	13.0 (8.1)	19.4 (11.3)	11.8 (7.7)
% drinking days	72.8 (23.5)	82.1 (1.3)	50.7 (29.7)
% heavy drinking days	65.2 (24.9)	79.0 (1.3)	45.8 (29.7)
Number of days since last drink	7.7 (5.3)	22.1 (4.4)	24.8 (16.1)
Medications			
Acamprosate, N	608	172	443
Naltrexone, N	614	169	0
No active drug (placebo or no medication), N	466	85	0
Treatment outcomes			
3 month abstinence from any drinking, N(%)	293 (21.2)	194 (45.5)	132 (29.7)
3 month abstinence from heavy drinking, N(%)	432 (31.2)	210 (49.3)	168 (37.9)

For COMBINE and CITA, baseline consumption is based on 30 days prior to the start of medication, while for PREDICT it is based on 30 days prior to the onset of inpatient treatment, as proposed by Mann and colleagues (84).

For the COMBINE study, the number of participants for each medication may include participants on more than one medication (i.e. groups are not mutually exclusive since the study included acamprosate/naltrexone co-treatment).

Numbers for treatment outcomes are based on the ITT sample (i.e. complete sample) assuming those who dropped out prior to 3 months had returned to heavy drinking.

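### Aim 1a compares outcomes through separate heritability intervals although they come from the same patients; a paired difference would be about 1.75 times more precise for the one pair that can be checked

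*Combined protocol and SAP*

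**What the plan says.** Under Analysis for Specific Aim 1a, the plan uses a "linear mixed model with residual maximum likelihood (REML) analysis to estimate the variance attributable to the SNPs", one outcome at a time, in a subsample of European ancestry. The outcomes are given as examples: "e.g. length of sobriety, return to heavy drinking or percent days abstinent". On pooling it says: "These analyses will include study, and principal components that capture ancestry as covariates". I read this as one fit per outcome across COMBINE, PREDICT and CITA.

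The comparison itself is a single sentence: "Estimates (and confidence intervals) for the SNP heritability of different outcomes will be compared". There is no standard error or interval for a difference, no joint model and no rule for calling one outcome more heritable than another.

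Specific Aim 1a states the use of the result: "These analyses may help determine if sobriety or another treatment outcome (e.g. return to heavy drinking) is the most suitable phenotype". Specific Aim 2a takes sobriety as primary and draws its other outcomes from Aim 1a.

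**The concern.** The quantity that bears on the choice of phenotype is the difference in heritability between two outcomes. Its variance is the sum of the two variances minus twice the covariance of the estimates. With the same patients and the same relationship matrix, that covariance is positive whenever the outcomes are correlated, and it can be large. Two separate intervals do not contain it. Anyone working from them alone has to drop the term, or look at overlap, which is stricter still.

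The resulting error goes one way. It does not create false differences; it hides differences that the data could show. For an analysis meant to discriminate between phenotypes, that is the less useful direction.

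**Working it through.** The plan states no precision or power for this comparison, so there is no figure to reproduce.

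**Inputs.** Table 2 gives, by study, "3 month abstinence from any drinking, N" (p1) and "3 month abstinence from heavy drinking, N" (p2). Dropouts are coded by "assuming those who dropped out prior to 3 months had returned to heavy drinking", so they fail both outcomes, and any-drinking abstainers are a subset of heavy-drinking abstainers.

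**Step 1: correlation of the pair.** For nested yes/no outcomes, phi² = p1(1 − p2) / [p2(1 − p1)].

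**Step 2: correlation of the estimates.** Each heritability estimate is driven by products of standardised outcomes over pairs of patients. For two outcomes with correlation r, these products correlate at r × r. The two estimates therefore correlate at about r² (an approximation).

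**Step 3: over-width.** With equal standard errors, SE(difference) is √2·SE if independence is assumed and √[2(1 − r²)]·SE if paired. The ratio is 1/√(1 − r²), whatever the SE.

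| Study | p1 | p2 | phi² | phi | Factor |
|---|---|---|---|---|---|
| COMBINE | 293/1393 = 0.210 | 432/1393 = 0.310 | 0.593 | 0.77 | 1.57 |
| PREDICT | 194/426 = 0.455 | 210/426 = 0.493 | 0.860 | 0.93 | 2.67 |
| CITA | 132/443 = 0.298 | 168/443 = 0.379 | 0.695 | 0.83 | 1.81 |

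**Step 4: pooled fit.** With study as a covariate, within-study terms are summed. Using the Table 2 percentages and sample sizes:
- covariance, Σ n·p1(1 − p2) = 203.2 + 98.3 + 81.7 = 383.2
- variance of the first outcome, Σ n·p1(1 − p1) = 232.7 + 105.6 + 92.5 = 430.8
- variance of the second, Σ n·p2(1 − p2) = 299.0 + 106.5 + 104.3 = 509.8
- r² = 383.2² / (430.8 × 509.8) = 0.668, so r = 0.82 and the factor is 1.74

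Other weights change little: white non-Hispanic counts (1062, 426, 412) give 1.77; acamprosate-treated counts (608, 172, 443) give 1.74; weights that sum to the stated total of 1687 (816, 426, 445) give 1.80.

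**Step 5: check of Step 2.** REML was simulated with 1687 patients, a variance of 2 × 10⁻⁵ for the off-diagonal relationships (assumed), 500 runs per setting, and true liability heritability of 0 and 0.3. Factors were 1.76 to 1.79 at the pooled rates, 1.48 to 1.54 for COMBINE, 1.71 to 1.87 for CITA and 2.73 to 2.79 for PREDICT.

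**Step 6: other outcomes.** No correlations are given for length of sobriety or percent days abstinent. Assumed r of 0.5, 0.7, 0.8, 0.9 and 0.95 gives factors of 1.15, 1.40, 1.67, 2.29 and 3.20.

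**Step 7: absolute precision.** The SE of one estimate is about √[2/(N²·v)], where v is the variance of the off-diagonal relationships. For N = 1687 and v from 1.5 × 10⁻⁵ to 3 × 10⁻⁵ (assumed), it is 0.22 to 0.15. The 95% half-width of a difference is then 1.96 × √2 × SE = 0.42 to 0.61 if independence is assumed. Divided by 1.75, it is 0.24 to 0.35.

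As an illustration, take an SE of 0.18 and a paired test. A true difference of 0.3 is detected with about 54% power, against 9% for a z-test that assumes independence. For a true difference of 0.1, paired power is only about 10%.

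**The case against.** The strongest reply is that the plan never states a wrong error bar. It claims no independence, sets no overlap rule and fixes no threshold; it says only that estimates and intervals will be compared. That is correct. The point is that the named inputs cannot yield the right uncertainty, not that a faulty interval has been specified.

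A reader might infer from the table in the working that the error reaches 2.7. The documents do not support that: 2.67 belongs to PREDICT alone, while the planned fit includes study as a covariate. Nor does the nested structure extend to every outcome. It describes one yes/no pair, and coding dropouts as failing both outcomes raises the agreement within that pair.

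A reader might also infer that the comparison cannot inform the choice of phenotype. This too goes beyond the text. Aim 1a only may help with that choice, the Endpoints section already fixes continuous sobriety as primary, and point estimates remain informative without a test.

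Finally, pairing does not make the comparison precise, as Step 7 shows. This stands, and it limits the gain. It is not a reason to use a standard error larger than the data require.

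**Conclusion.** The concern holds in a limited form. Followed as written, Aim 1a gives a less precise contrast between outcomes than the same data allow. For the two abstinence outcomes of Table 2 in the pooled fit, the standard error of the difference would be overstated by about 1.75 (1.74 to 1.80 by choice of weights). For other pairs the direction is the same for any non-zero correlation, but the size cannot be taken from the documents.

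The result rests on three assumptions: the r² approximation, which simulation supports; roughly equal standard errors for the two outcomes; and Table 2 proportions carrying over to the European-ancestry subsample. The absolute widths rest further on an assumed relationship-matrix variance.

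The error is conservative, lies in a secondary analysis of existing data, and does not affect the trial's own treatment estimates. It is still worth correcting, because the contrast is what the analysis offers to the choice of further Aim 2 outcomes.

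**What to change.** Replace the comparison sentence under Analysis for Specific Aim 1a with:

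> Outcomes will be compared by the estimated difference in SNP heritability, with a confidence interval that accounts for their covariance, from bivariate GREML in GCTA for each pair of outcomes, or from a delete-block jackknife over patients applied to the difference if the bivariate model does not converge.

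The genetic correlation may be added as a description. A value near 1 should not be read as showing that the choice of outcome matters little, because heritability, and with it GWAS power, can still differ.

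The cost is one sentence and a few extra runs in software the plan already names, with no new data. The downside is possible non-convergence for highly correlated pairs, which the jackknife is there to cover.

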#### Analysis for Specific Aim 1b

Metabolite concentrations will be log-2 transformed, and associations between baseline metabolite concentrations and the time of abstinence since baseline will be evaluated by linear regression with age and gender as covariates. If Timeline Follow Back (TLFB) data at 3-months is absent, the date of last contact will serve as the day of first lapse unless the subject has reported a lapse at an earlier time point. To study the possible effect of depression severity and liver function, regression models including baseline PHQ-9 scores and LFTs (AST, ALT, and GGT) will be compared with those without to determine whether the metabolites remain significantly correlated with treatment outcome. Participants who provided paired blood samples will be classified as responders (maintenance of complete abstinence) or non-responders (any consumption of alcoholic beverages during the trial period), and their metabolite concentrations at baseline and at 3 months will be compared by two-way ANOVA to detect any significant changes between the two time points and whether these changes differ significantly between groups.

After metabolomic markers associated with length of sobriety (or additional secondary phenotypes) are identified, we will apply a “pharmacometabolomics-informed pharmacogenomics” research strategy. Specifically, we will perform genome-wide association analyses to search for genetic variants associated with metabolites that are associated with acamprosate clinical outcomes. We will then evaluate the association of the identified genetic variants ( $p < 5 \times 10^{-8}$ ) with clinical treatment outcomes in all available datasets (including the COMBINE and PREDICT datasets used in Aim 1a). We will also pursue all signals, genes and pathways functionally and mechanistically in order to investigate the biological mechanisms underlying sobriety length and other phenotypes associated with acamprosate treatment response. This is the same approach that we used previously with success to study biological mechanisms contributing to effects of selective serotonin reuptake inhibitors in patients with major depressive disorder (MDD).

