assessment of patient's treatment needs. In our experience only 15-20% of patients choose to add acamprosate to their treatment.

Clearly, response predictors are needed to improve treatment and it is expected that pharmacogenomic research will aid in the discovery of such predictors [7, 8]. Moreover, the discovery of biological mechanisms of response to acamprosate as a "probe drug," may guide development of innovative treatment approaches and personalized recommendations for the treatment of patients with AUD.

We previously demonstrated an association of the glutamate ionotropic receptor N-methyl-D-aspartate (NMDA) type subunit 2B (*GRIN2B*) rs2058878 variant with sobriety length in two independent samples of acamprosate-treated alcoholics [9]. Yet, these findings were based on a candidate gene/pathway approach and potentially missed other important variations, suggesting a need for an unbiased and comprehensive search for genetic markers of response. Moreover, although clinical data favors sobriety as a treatment outcome associated with acamprosate, no studies have explored whether sobriety is more heritable than other alcoholism treatment outcomes, and thus it is unknown whether sobriety is the most appropriate outcome for pharmacogenomics investigations. Furthermore, the intermediate phenotypes, which are more proximal to genetic variation compared to behavioral phenotypes, are known to improve the power of genetic association studies [10, 11]. We have previously demonstrated that change in the plasma metabolite levels is a powerful intermediate phenotype allowing for the identification of genes associated with treatment response to selective serotonin reuptake inhibitor (SSRI) antidepressants – an approach called 'pharmacometabolomics-informed pharmacogenomics' [12]. However, this powerful approach has not been used in pharmacogenomic studies of antidipsotropic medications. Yet, preliminary metabolomic analyses of our data indicated that acamprosate responders had elevated serum glutamate at baseline, which decreased during treatment [13]. Similarly, our brain imaging studies showed an association of glutamate levels in the left dorsolateral prefrontal cortex with alcohol cravings and response to acamprosate treatment [14, 15].

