- (1) We will standardize depression and anxiety treatment by accepting current and stable use of SSRI & SNRI medications listed in table 3 (page 14) in all participants with depression and/or anxiety diagnoses. This will allow for an assessment of the impact of depression and/or anxiety as well as their standardized treatment on acamprosate and placebo-related treatment outcomes and account for this impact in genetic and metabolomic association analyses. Patients with newly diagnosed anxiety or depression as well as patients with known diagnosis but not taking any antidepressant will be offered treatment with escitalopram or citalopram as first line treatment during study participation when their GAD-7 or PHQ-9 scores are equal or above 10. We selected escitalopram based on evidence suggesting it is strongest among selective serotonin reuptake inhibitors (SSRIs) [18] and favoring it over other antidepressants in terms of efficacy and tolerability [19]. Clinical findings in adults with AUD and depression as well as our experimental data also suggest that the combined use of escitalopram and acamprosate may improve treatment outcomes [20, 21]. This threshold has been chosen based on previous research showing that PHQ-9 score  $\geq 10$ , indicative of the presence of at least moderate depression and/or a GAD-7 score of  $\geq 10$ , indicative of the presence of at least moderate anxiety reflect a clinically significant level of symptom severity warranting the use of medications [16, 17]. Results of treatment with escitalopram or citalopram will be monitored by the study

psychiatrist affiliated with each study site who will make appropriate treatment recommendations as described below.

[figure not shown]
(2) To avoid the impact of end stage liver disease on clinical and metabolomic findings, we will use a Model for End-Stage Liver Disease (MELD) score of 10 and below as a cut off for *inclusion* in the study, and will *exclude* patients with a diagnosis of advanced liver disease or those with a MELD score above 10, which is considered an indication that the extent of liver damage has reached an advanced stage [22, 23]. The MELD score will be calculated according to the standard approach using serum concentrations of bilirubin and creatinine, and the international normalized ratio for prothrombin time [22].

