Other location's (Mayo Clinic Rochester & Hazelden Betty Ford, Center City, MN) patients' blood volume per blood draw: 50ml at Baseline (preferred but can be done at any visit) and 35 ml at Months 1 & 3

Hazelden Center City will offer participants to provide the additional ~15ml of blood as optional (preferred at baseline visit but can be done at any visit) for generation of the induced pluripotent stem cells (iPSCs) from peripheral blood mononuclear cells (PBMC) as described below.

Frequency of blood draw: three time points, Baseline, 1 and 3 month visits.

Blood samples for 35ml collection are for GGT levels: Serum Separator Tube (SST); DNA extraction, Acamprosate blood levels, Metabolomic, Proteomic biomarkers (EDTA tubes), and mRNA (PAXGene tube). The process of spinning and aliquoting the samples will be completed at each site. EDTA tubes that would need to be kept on ice, centrifuged in the cold (NOT frozen) with the plasma aliquoted into 200 ul aliquots which would need to be immediately placed and stored at minus 80 degrees. The current metabolomic platform would include both the amines and neuromodulators. Acamprosate blood drug levels will be plasma aliquoted into 300 ul aliquots and also assayed with these samples. PAXGene tube is placed directly into the minus 80 degree freezer.

An additional 15 ml of blood collected in EDTA tubes for peripheral blood mononuclear cells (PBMC) isolation. The separation and banking of PBMCs will be performed in the laboratory, frozen and stored in liquid nitrogen. PBMC are used to generate induced pluripotent stem cells (iPSCs), a cell type that can self-renew and which can be differentiated into many cell types from many human tissues.

## Review of medical records, images, specimens – Category 5

**For review of existing data:** provide a date range or an end date for when the data was generated. The end date can be the date this application was submitted to the IRB. Example: 01/01/1999 to 12/31/2015 or all records through mm/dd/yyyy.

**Date Range:** 12/29/2004 to 07/09/2013

Check all that apply (data includes medical records, images, specimens).

(5a) Only data that exists before the IRB submission date will be collected.

(5b) The study involves data that exist at the time of IRB submission **and** data that will be generated after IRB submission. Include this activity in the Methods section.

(5c) The study will use data that have been collected under another IRB protocol.

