### ***Limitations and Proposed solutions***

- The proposed study design may not allow for the separation of the effects of depression and anxiety from the treatment effects of SSRIs, and SNRIs listed on an association between genetic variation and acamprosate or placebo-related treatment outcomes. Separation of those effects would have required an additional placebo arm for antidepressant treatment. We considered this option but concluded it would not be feasible and may negatively affect the attainment of the primary study goal - i.e. identification of genetic markers associated with acamprosate-related treatment outcomes in participants with AUD. Therefore, the difference between the effects related to presence/severity of depression or anxiety and the effects of antidepressant treatment on an association between genetic variation and acamprosate or placebo-related treatment outcomes will need to be investigated in future studies.
- Although the size of the new study sample proposed for the pharmacogenomic analyses in Aim 2 is comparable or exceeds the size of samples collected for the CITA, COMBINE and PREDICTS studies, this sample alone is still unlikely to provide sufficient power to detect significant associations. However, as described above, our goal is to conduct a meta-analysis to identify pharmacogenomic markers associated with response to acamprosate in a combined sample including participants enrolled as part of the proposed center as well as those collected in the COMBINE, PREDICT and CITA studies. This will be the largest pharmacogenomics GWAS in AUD to date. Moreover, the sample will also include a large set of placebo-treated participants ( $N \approx 800$ ) allowing for differentiation between acamprosate-specific pharmacogenomic effects from treatment independent predictors of abstinence in patients with AUDs.

We also expect that the application of pharmacometabolomics- and imaging-guided pharmacogenetic analyses of the acamprosate-related outcomes described in Aim 3 will allow for the use of intermediate phenotypes (namely metabolomic and neuro-imaging signatures associated with acamprosate response) and will improve the power for the discovery of genetic variations predictive of response to acamprosate.

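### The Aim 2b metabolite models name no antidepressant term, although the protocol commits to accounting for that treatment in the metabolomic analyses

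*Combined protocol and SAP*

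**What the plan says.** The model is set out under Analysis for Specific Aim 1b: "associations between baseline metabolite concentrations and the time of abstinence since baseline will be evaluated by linear regression with age and gender as covariates". To examine depression severity and liver function, "regression models including baseline PHQ-9 scores and LFTs (AST, ALT, and GGT) will be compared with those without". For participants with paired samples, classified as responders (complete abstinence) or non-responders (any drinking), "metabolite concentrations at baseline and at 3 months will be compared by two-way ANOVA"; no covariate is named. Analysis for Specific Aim 2b adopts a similar strategy for the new trial and adds an assessment of whether metabolite predictors differ between acamprosate and placebo.

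The antidepressant rules for the new trial are in Assessments, item (1). Current, stable SSRI or SNRI use is accepted. Patients with depression or anxiety who take no antidepressant and score 10 or more on PHQ-9 or GAD-7 "will be offered treatment with escitalopram or citalopram as first line treatment during study participation". The same item says that this standardization will let the study assess the impact of depression, anxiety and their treatment, and "account for this impact in genetic and metabolomic association analyses".

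Limitations and Proposed solutions concedes that the design "may not allow for the separation of the effects of depression and anxiety from the treatment effects of SSRIs" and SNRIs, but words this for associations with genetic variation.

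**The concern.** The commitment covers the metabolomic analyses, yet the metabolite models contain no term for the treatment. PHQ-9 does not stand in for it. It measures current symptoms, so a well-controlled SSRI user and an untreated person without depression can have the same score and different drug exposure. GAD-7, the other trigger for offering treatment, does not appear in the metabolite models at all.

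The documents make both links needed for confounding plausible. On the metabolite side, the Background says of SSRI treatment that "change in the plasma metabolite levels is a powerful intermediate phenotype", and the Biospecimens text states: "The current metabolomic platform would include both the amines and neuromodulators". On the outcome side, Assessments item (1) says that escitalopram combined with acamprosate may improve treatment outcomes.

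At stake is which metabolites Aim 2b reports as predictors of sobriety and takes forward to genome-wide analysis. A metabolite that mainly marks antidepressant use could be among them.

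**Working it through.** The plan gives no figure on this point to reproduce. The check asks which analysis each kind of exposure can reach, and then how large the effect could be.

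**1. Which exposure reaches which analysis**

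- *Use already present at the baseline draw.* This can affect the baseline regression, because stable users are enrolled.
- *Starts after the baseline draw.* PHQ-9 and GAD-7 are taken at every contact (Table 1) and blood is drawn at baseline, month 1 and month 3, so a start can fall between the paired samples. It cannot alter a sample already taken. A simulation with post-baseline starts only (20% starting, 0.4 SD effect on outcome, n=445) gave a rejection rate of 0.056 in the baseline regression, against a nominal 0.05. Only the paired ANOVA is exposed.

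**2. Baseline regression: size under assumed inputs**

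The documents give no use rate, metabolite shift or outcome effect. Assume a proportion p of users, a metabolite shift of d SD in users, and a difference of δ SD in abstinence length, with no true metabolite effect. Then

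r = p(1−p)dδ / √{[1+p(1−p)d²][1+p(1−p)δ²]}, z = r√n,

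and the two-sided 5% test rejects with probability P(Z > 1.96−z) + P(Z < −1.96−z).

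Example: p=0.35, d=1, δ=0.3 gives p(1−p)=0.2275 and r = 0.06825/√(1.2275×1.0205) = 0.061. At n=800, z = 0.061×28.28 = 1.73 and the rejection rate is 41%.

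Rejection rates at n=800:

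| p | d=0.5, δ=0.15 | d=0.5, δ=0.3 | d=1, δ=0.15 | d=1, δ=0.3 |
|---|---|---|---|---|
| 0.20 | 6% | 10% | 10% | 24% |
| 0.35 | 8% | 15% | 14% | 41% |
| 0.50 | 8% | 17% | 16% | 47% |

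Nine of the twelve scenarios lie at 6-17%. The other three need both the larger shift and the larger outcome difference. If δ=0, then r=0 and the rate is 5%. Within the acamprosate arm at 2:1, n = 800×2/3 ≈ 533 and the 41% falls to 29%.

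A separate simulation (2,000 runs per setting, n=445, use 20-40%, shift 0.3-0.8 SD) agrees. Without the term the rate was about 0.05 when use was unrelated to outcome, 0.05-0.11 at an outcome effect of 0.2 SD, and 0.06-0.32 at 0.4 SD. With the term it was 0.04-0.06 throughout.

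**3. Paired ANOVA**

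False time-by-response difference = (start rate in non-responders − start rate in responders) × d. With assumed rates of 20% vs 10% and d=0.5 this is 0.10×0.5 = 0.05 SD; with 25% vs 10% and d=1 it is 0.15×1 = 0.15 SD. In simulation (150-500 pairs, one third responders, shift 0.5-0.8 SD), the rejection rate was about 0.05 with equal starts (10% each), 0.06-0.12 at 10% in responders vs 20% in non-responders, and 0.08-0.35 at 5% vs 25%.

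**4. Metabolite-by-arm interaction**

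With n=800 at 2:1, use balanced between arms and the same antidepressant effect in both arms, the rejection rate was 0.045-0.062. Balance is less assured after the 5-12-2023 notation, because later enrollees all receive acamprosate and have no concurrent placebo group.

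**The case against.** The strongest reply is that Aim 2b promises a similar strategy, not an identical model, and that the commitment in Assessments item (1) already binds the analyst. That narrows the point to a commitment without a named term, but the only covariates actually written for the metabolite models leave the drug out. The covariate list for the SNP models in Aim 2a is open-ended and could admit antidepressant use, so the point does not extend to those models.

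Three stronger readings are tempting, and the documents do not support them.

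- *That the CITA analysis in Aim 1b is shown to be confounded.* CITA was recruited earlier under another protocol. The item (1) rules govern the new trial, and antidepressant use in CITA is not described.
- *That antidepressant effects will be read as acamprosate-specific markers.* The Aim 2b comparison between arms largely guards against this when use is balanced.
- *That a false metabolite carries straight through to a genetic finding.* A selected metabolite must still yield a variant at p<5×10⁻⁸, which is then tested against clinical outcomes in other datasets. The documents give no reason why antidepressant use should track genotype.

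It is also fair that this is discovery work and that a limitation is disclosed. But that limitation is worded for genetic associations, and adjusting for drug exposure does not require separating illness from treatment.

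One objection changes the remedy. Starting an antidepressant may follow relapse or worsening mood, so adjusting for it or excluding starters conditions on an event after baseline that may be related to response.

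**Conclusion.** The concern holds for Aim 2b: the stated metabolite models do not carry out the protocol's own commitment, and PHQ-9 does not fill the gap. Overall and within-arm associations with baseline metabolites are exposed to antidepressant use at the baseline draw, provided that use relates to both metabolite and outcome. The paired ANOVA is exposed to starts between draws, provided that they differ by responder status. The metabolite-by-arm test is largely protected under balanced use and a similar antidepressant effect in both arms, and less so for enrollees after the 5-12-2023 notation.

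The size cannot be established from the documents. The range of about 5% to 47% rests wholly on assumed inputs. A reader might take the 41-47% values as expected error rates, but they are corner cases.

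**What to change.** - In Analysis for Specific Aim 2b, add antidepressant use at the time of the baseline draw (yes/no, or class) as a covariate in the metabolite-outcome models, and add GAD-7 beside PHQ-9 in the comparison models. Do the same for CITA under Aim 1b only if the data exist.
- For the paired comparison, keep the main analysis. Add a sensitivity analysis that flags or excludes participants who started or changed an antidepressant between draws, labelled as conditioning on a post-baseline event.
- Extend the statement in Limitations and Proposed solutions to the metabolite analyses.
- State where antidepressant use and start or change dates are recorded; Table 1 as read shows no concomitant-medication row.

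The cost is one or two parameters with a small loss of precision, plus dates drawn from study records. Baseline use should already be known from eligibility assessment. Treatment rules are unchanged.
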